### **Statistical methods**

Demographics and perioperative characteristics of this cohort will be summarized using the standard summary statistics.

We will use a linear mixed effect model with repeated measures to estimate the correlation between (1) SVC diameter and (2) SVC collapsibility index and simultaneously measured CVP across over the five measurement times, including before surgical incision, start of preanhepatic phase, start of anhepatic phase, start of postanhepatic phase, and after closure of deep fascial layer of the anterior abdominal wall (13). In the mixed model, an unstructured covariance matrix will be used to account for within-patient correlation. The significance criterion will be 0.025 for each analysis; thus 97.5% CI will be reported (i.e., 0.05/2, Bonferroni correction).

In addition, we will assess whether the correlation between SVC diameter and SVC collapsibility index and CVP differs over measurement time (time interaction) using a separate linear mixed effect model with a time interaction term. Regardless of the significance of the interaction, we will report the correlation coefficient at each of the five measurement times along with 99.5% confidence interval (i.e., 0.025/5, Bonferroni correction) for information purpose.

Secondly, we will also assess whether the correlation between SVC diameter and SVC collapsibility index and CVP differs between patients with and without normal pulmonary artery pressures and normal right ventricle function. If the above interaction exists, we will report the correlation separately.

The changes in SVC diameter and SVC collapsibility index that occur with inferior vena cava cross clamping during liver transplant will be summarized.

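### The time interaction term, as ordinarily fitted, compares slopes or mean profiles across phases, so it tests equality of the five SVC-CVP correlations only if the SD ratio is constant

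*Combined protocol and SAP*

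**What the plan says.** All of this is in the combined protocol and SAP, under Statistical methods.

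- Main analysis: "We will use a linear mixed effect model with repeated measures to estimate the correlation between (1) SVC diameter and (2) SVC collapsibility index" and simultaneous CVP, where "an unstructured covariance matrix will be used to account for within-patient correlation". A methods reference on estimating correlation with repeated measures is attached to this sentence.
- Phase comparison: the plan will assess whether the correlation with "CVP differs over measurement time (time interaction) using a separate linear mixed effect model with a time interaction term". It does not name the response, write out the model, say what time is interacted with, or mention standardising within phase or contrasting correlations.
- Reporting by phase: "Regardless of the significance of the interaction, we will report the correlation coefficient at each of the five measurement times along with 99.5% confidence interval", but only "for information purpose".
- Comparison of patients with and without normal pulmonary artery pressure and RV function: "If the above interaction exists, we will report the correlation separately".

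The criterion is 0.025 for each SVC measure. No alpha is stated specifically for the interaction test.

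**The concern.** The question is about correlations, which are symmetric and scale-free. The named tool is an interaction coefficient, which is neither. In a regression of CVP on SVC it compares slopes, and slopes also move with the spread of either variable. The plan could therefore report that the correlation changes by surgical phase when only the SD ratio changes, or miss a real change that the SDs offset.

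The documents give reasons why the ratio might change. Aim 2 concerns cases done with IVC cross-clamping, which implies that some are not, so the anhepatic readings may mix clamped and unclamped patients. The Introduction describes postanhepatic CVP rises linked to pulmonary pressure or RV decline, which need not occur in every patient. Neither shows that the ratio does change.

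The phase-specific correlations are informational, so the interaction is the only formal test of a phase difference. In the pulmonary-pressure/RV comparison the interaction also decides what is reported.

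**Working it through.** **1. The plan's own figures.** Sample Size Considerations gives 97.5% CI widths for a Pearson correlation. With tanh(atanh(r) ± z/√(n−3)) and z = 2.241:
- n = 500: 0.1925 at r = 0.2 and 0.1507 at r = 0.5 (stated 0.19 and 0.15).
- n = 100: 0.4304 and 0.3398 (stated 0.43 and 0.34).

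These reproduce. The plan gives no size or power for the interaction test.

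**2. Inputs.** From the documents: 100 patients, five paired readings each, unstructured covariance, 0.025 per SVC measure. Assumed: 0.025 also applies to the interaction; normal data; the within-patient correlations, SD ratios and mean shift shown below. The documents give no mean or SD for CVP or SVC at any phase.

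**3. The identity.** For CVP regressed on SVC, slope at time t = r_t x SD(CVP)_t / SD(SVC)_t. With SD(SVC) = 1 throughout:
- r = 0.4 at all times, CVP SD 1 then 1.5: slopes 0.4 and 0.4 x 1.5 = 0.6. Equal correlations, unequal slopes.
- r = 0.6 with CVP SD 1, r = 0.3 with CVP SD 2: slopes 0.6 and 0.3 x 2 = 0.6. Unequal correlations, equal slopes.

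**4. False rejection when all five correlations are 0.4.** Slope-by-time test by generalised least squares with unstructured residual covariance, CVP as response, SD change at the last two times, within-patient correlation 0.3 / 0.6:

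| SD change | Rejection at nominal 2.5% |
|---|---|
| none | 2.1% / 3.2% |
| CVP x1.25 | 8.0% / 14.7% |
| CVP x1.5 | about 25% / 45% |
| CVP x2 | 60.4% / 84.9% |
| CVP and SVC both x1.5 | 2.7% / 4.2% |

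The last row shows that the ratio matters, not CVP spread alone. The choice of response matters too. With the SVC SD halved in the anhepatic phase only (within-patient correlation 0 / 0.5), rejection is 28% / 48% with CVP as response and 58% / 84% with SVC as response.

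**5. Power when r is 0.6 at three times and 0.3 at two.** CVP as response, within-patient correlation 0.3 / 0.6:

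| CVP SD at the low-r times | Slope test |
|---|---|
| x0.75 | 99.8% / 100% |
| equal | 87% / 99% |
| x1.25 | about 45% / 70% |
| x2 (slopes cancel) | 3% / 5% |

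A direct test on the Fisher-z correlations gives about 90-98%. Its size under equal correlations was 2.4% to 4.8% over the scenarios run, so the robust Wald version is slightly liberal at n = 100.

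**6. Stacked-outcome reading.** A variable-type-by-time fixed effect compares mean profiles. With r = 0.4 throughout and the CVP mean 0.5 SD lower in the anhepatic phase, it rejects in 85% / 99.8% (within-patient correlation 0 / 0.5). With r = 0.5 at four phases, 0.2 in the anhepatic phase and no mean change, it rejects in 1.5% to 3.3%.

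**7. The informational intervals.** At n = 100 the 99.5% CI is 0.535 wide at r = 0.2 and 0.424 at r = 0.5. They show the estimates but do not test a difference.

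These are 600 to 1,500 runs per cell for the slope test. Simulation error is about ±1 point near 2.5% and up to ±4 points near 50%.

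**The case against.** The strongest reply is that the model is underspecified rather than shown to be wrong. The text says that the correlation is to be assessed, and the main analysis cites a method for estimating correlations. A version that does test correlations, such as slopes on values standardised within phase, is not excluded; that version rejected in 1.0% to 2.7% under equal correlations. This stands as a limit on certainty. But the citation is attached to the main model, the interaction model is described as separate, and nothing in the text specifies a valid version.

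A reader might infer that the slope test has almost no power whenever the correlation changes. That is not so: at equal SDs it has 87-99% in the setting above, and near-null power needs SD changes that offset the change in correlation. Nor does it mis-state error whenever CVP spread changes, since scaling both SDs together left it near nominal. With CVP as response and a constant SD ratio, the test is nearly harmless. (With SVC as response, one equal-SD scenario, r 0.5 versus 0.2 and within-patient correlation 0.5, gave 26% power against 81% with CVP as response.)

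A reader might also infer that the five phase correlations depend on the interaction term. The plan promises them regardless of its result and does not say that the term produces them.

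Finally, this is an additional analysis. The primary correlations, their 97.5% CIs and the sample-size rationale are untouched, which limits the severity.

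**Conclusion.** The point holds in a limited form. The only named test of a phase difference in correlation would, as ordinarily fitted, test slopes or mean profiles. It answers the stated question only under a constant SD ratio, which the documents do not state. False rejection is about 25% to 45% under the assumed 1.5-fold CVP SD change and near nominal when the ratio is constant. Power runs from above that of a direct test to almost none, depending on the SDs. Every SD ratio is an assumption, so these figures show a range and do not predict this trial.

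The documents do not support the stronger readings that the phase conclusion will be wrong or that the main result is compromised. The consequence is greater in the pulmonary-pressure/RV comparison, where the interaction decides whether separate correlations appear. No calculation was made for that comparison; the argument there rests on the slope identity alone. Rating: should-fix.

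**What to change.** 1. State the null as equality of the five SVC-CVP correlations, separately for diameter and collapsibility index.
2. Test it directly, with SDs free to differ by time. Either use a 4-df likelihood-ratio test of five free correlations against one common correlation in the two-outcome repeated-measures model, or a Wald test on the five Fisher-z values with a patient-level bootstrap.
3. State the alpha for this test. If a robust Wald version is used, note that its size at n = 100 is about 2.5-5% at nominal 2.5%.
4. Take the per-phase correlations and their 99.5% CIs from the same analysis.
5. Use the same kind of test, by group, for the pulmonary-pressure/RV comparison.
6. If the interaction term is kept, write out the model, name the response, and label the result as a test of slopes.

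The cost is SAP wording and some extra code, with no new data. It should be settled before the data are analysed.

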**Significance:**

While most centers utilize central venous catheters or pulmonary artery catheters during liver transplant surgery, (3) there are complications associated with central invasive catheter use. (10)

If SVC collapsibility index is correlated with CVP measurements, it would allow:

- 1- Less reliance on central invasive catheter use especially in select population of liver transplant recipients especially those with normal pulmonary artery pressures and normal right ventricle function. Large bore peripheral venous catheters that allow rapid administration of fluids and blood products would substitute central venous catheter use with transesophageal monitoring of SVC diameter and collapsibility for calculation of pulmonary artery systolic pressure (PASP).
- 2- Noninvasive measurement of PASP in mechanically ventilated patients with no central venous monitoring (not just in patients undergoing liver transplantation) especially that IVC measurement in mechanically ventilated patients may be inaccurate in identifying CVP. (7) Since the SVC is entirely located intrathoracic its collapsibility with positive pressure ventilation makes it an attractive method of non-invasively estimating CVP.(8)
- 3- There are no studies that identify the changes in SVC diameter and collapsibility index during IVC cross- clamping (during the anhepatic phase of liver transplant surgery). This study will provide insight to changes in SVC diameter and collapsibility index in response to IVC crossclamping during the anhepatic phase.

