**Aim of the study:**

- 1- To assess the correlation of SVC diameter and SVC collapsibility index measurements obtained intraoperatively by Transesophageal echocardiography (TEE) with simultaneous CVP measurements obtained and recorded electronically ( via an automated intraoperative record keeping system) through a centrally inserted central venous catheter or a right atrial port of a pulmonary artery catheter
- 2- To identify the changes in SVC diameter and SVC collapsibility index that occur with inferior vena cava cross clamping during liver transplant cases performed using IVC cross clamping

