**Methods:**

Following RAC and IRB approval, consecutive patients undergoing liver transplant surgery will be included in the study. We will ask the IRB for informed consent waiver since both TEE and central venous monitoring are used routinely in liver transplant recipients.

Simultaneous measurements of SVC diameter, SVC collapsibility index, CVP (captured electronically through an automated record keeping system) will be recorded by experienced anesthesiologists with expertise and qualifications in Transesophageal Echocardiography. **Simultaneous cardiac output measurements (thermodilution) will also be recorded.**

Measurements of the SVC will be taken in the midesophageal bicaval view (90-110 degrees) using M-mode echocardiography, 1 to 2 cm away from the entry point into the right atrium. This technique is analogous to that recommended when measuring IVC diameter and collapsibility (7) and was previously described by Cowie et al. (8)

The maximum and minimal diameter of the SVC will be measured and recorded.

Collapsibility index of SVC, “SVC collapsibility index” which is a measure of the inspiratory decrease in SVC diameter will be determined based on the following formula

(Maximum diameter on expiration—minimum diameter on inspiration)/Maximum diameter on expiration, expressed as a percentage

Patients will be ventilated using Pressure Control Ventilation with a tidal volume of 6 to 8 ml/kg with a respiratory rate of 10-12/min and a positive end expiratory pressure of 5 to 8 cmH2O.

Measurements will be recorded during the following time periods:

- 1- Before surgical incision ( following induction of General Anesthesia and placement of invasive monitoring and TEE)
- 2- Preanhepatic phase
- 3- Anhepatic phase
- 4- Postanhepatic phase ( following reperfusion)
- 5- Following closure of the deep fascial layer of the anterior abdominal wall

Simultaneously, CVP will be recorded from the right atrial port of the pulmonary artery catheter or from the proximal port of a CVC inserted in the internal jugular vein

Patients will be placed in the supine position with pressure transducers zeroed to atmospheric pressure and located at the mid-thoracic position, half-way between the sternum and bed, as recommended in recent guidelines. (12)

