#### Sample Size Considerations

With 100 patients and 5 pairs of measurement per patients we will provide enough data to adequately study the accuracy. For example, the width of our 97.5% CI for Pearson correlation will range from 0.19 to 0.15 for correlations ranging from 0.2 to 0.5, respectively, assuming a within-subject correlation of 0 (i.e., equivalent to 500 independent patients). In the other of the extreme scenario (i.e., within-subject correlation of 1), the width of our 97.5% CI for Pearson correlation will range from 0.43 to 0.34 for correlations ranging from 0.2 to 0.5, respectively. Approximately 10 liver transplant cases per month are conducted at the Cleveland Clinic main campus. Thus, a plan of 100 patients is feasible within 1 year. SAS software version 9.4 for Windows (SAS Institute, Cary, NC, USA) will be used for all analyses.

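### The anhepatic correlation and the time-interaction test pool IVC-clamped and unclamped cases, so a sizeable technique difference could be mistaken for a phase effect; the primary overall correlation is affected little

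*Combined protocol and SAP*

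**What the plan says.** Under Methods, "consecutive patients undergoing liver transplant surgery will be included in the study". Neither the inclusion nor the exclusion criteria restrict the caval technique. Aim 2 concerns "liver transplant cases performed using IVC cross clamping", a restriction that makes sense only if some cases are done otherwise. Item 3 under Significance places the clamp in the anhepatic phase.

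Statistical methods gives three Aim 1 outputs over all patients:

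- an overall correlation from a mixed model with unstructured covariance, for which "The significance criterion will be 0.025 for each analysis; thus 97.5% CI will be reported";
- a separate model with a time interaction;
- whatever that test shows, "we will report the correlation coefficient at each of the five measurement times along with 99.5% confidence interval" ("i.e., 0.025/5, Bonferroni correction) for information purpose").

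The only patient characteristic examined as a modifier is pulmonary artery pressure with right ventricular function. Clamping enters only a descriptive summary of changes in SVC diameter and collapsibility, which leaves out CVP. Clamp status is not among the measurements that Methods lists for recording.

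**The concern.** At four of the five reading times the patients are in broadly the same state with respect to the clamp. At the anhepatic reading they may be in two: IVC clamped or not. Pooling two groups with different means changes a correlation even when the relation within each group is the same. If the clamp moves CVP and the SVC measure in the same direction, the gap between the groups adds to the correlation. If it moves only one of them, or moves them in opposite directions, it dilutes the correlation. Phase means in the model do not remove this, because the split lies inside one phase.

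At stake is how two outputs are read: the anhepatic correlation, and any finding that the correlation differs over time. Either could reflect this centre's mix of techniques and not how closely the SVC tracks CVP in that phase. Because the clamp summary omits CVP, the planned output would not let a reader check.

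**Working it through.** **Inputs from the documents.** Sample Size Considerations: "With 100 patients and 5 pairs of measurement per patients", with correlations of 0.2 to 0.5. Statistical methods: alpha 0.05/2 = 0.025 per analysis, and 0.025/5 = 0.005 per time point.

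**Inputs assumed.** Clamped share p, and clamp shifts dC (CVP) and dS (SVC measure) in within-group SDs. The documents give none of these, so ranges are shown.

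**Step 1: the plan's own figure.** The Fisher interval is tanh(atanh(r) ± z/√(n−3)), with z for two-sided alpha 0.025. With n = 500 the widths are 0.192 (r = 0.2) and 0.151 (r = 0.5). This matches the statement that "the width of our 97.5% CI for Pearson correlation will range from 0.19 to 0.15 for correlations ranging from 0.2 to 0.5". With n = 100 they are 0.430 and 0.340, matching the stated 0.43 and 0.34.

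**Step 2: pooled correlation at the anhepatic reading.** With the same correlation ρ within both groups and v = p(1−p):

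r = (ρ + v·dC·dS) / √[(1 + v·dC²)(1 + v·dS²)]

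Example with p = 0.5, dC = dS = 1, ρ = 0: v = 0.25, so r = 0.25/1.25 = 0.20.

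Equal shifts in the same direction:

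| ρ | p | d = 0.5 | d = 1 | d = 1.5 |
|---|---|---|---|---|
| 0 | 0.5 | 0.06 | 0.20 | 0.36 |
| 0 | 0.1 or 0.9 | 0.02 | 0.08 | 0.17 |
| 0.2 | 0.5 | 0.25 | 0.36 | 0.49 |
| 0.5 | 0.5 | 0.53 | 0.60 | 0.68 |

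Other patterns with p = 0.5, d = 1, ρ = 0.5:

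- opposite shifts: (0.5 − 0.25)/1.25 = 0.20;
- CVP shifts alone: 0.5/√1.25 = 0.45.

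The same formula serves the collapsibility index, with dS taken as the signed shift in the index. No separate figures were run for it.

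**Step 3: overall correlation.** One reading in five is affected, so with phase means removed and equal shifts, v·d² is divided by 5. For p = 0.5 and ρ = 0.30:

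- d = 1: (0.30 + 0.05)/(1 + 0.05) = 0.33;
- d = 1.5: (0.30 + 0.1125)/(1 + 0.1125) = 0.37;
- d = 2: (0.30 + 0.20)/(1 + 0.20) = 0.42.

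The narrowest interval the plan foresees has width 0.15, or about ±0.075. The 0.03 change at d = 1 is well inside that.

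**Step 4: time interaction.** Simulation with 100 patients, five times, intraclass correlation 0.5, p = 0.5, equal shifts in the same direction at the anhepatic time only, the same ρ at all times, and 2000 runs per scenario. A Wald test on Fisher z at 0.025 stood in for the plan's mixed-model test. Rejection rates:

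| ρ | d = 0 | d = 0.5 | d = 1 | d = 1.5 |
|---|---|---|---|---|
| 0 | 0.03 | 0.04 | 0.26 | 0.83 |
| 0.2 | 0.03 | 0.03 | 0.19 | 0.70 |
| 0.5 | 0.03 | 0.02 | 0.12 | 0.51 |

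When clamp-by-time means are removed, the rate is 0.022 to 0.034 in every scenario. With ρ = 0, the anhepatic 99.5% interval excludes 0 in 0.02, 0.21 and 0.84 of runs at d = 0.5, 1 and 1.5 (nominal 0.005). After removal it does so in 0.004 to 0.006.

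**The case against.** The strongest reply is that the within-technique correlation need not be the target. The hypothesis asks whether SVC measures correlate with CVP in liver transplant recipients. If the clamp lowers CVP and the SVC narrows because of that, the SVC is tracking CVP, and removing clamp means discards real variation. This stands in part. If the clamp acts on the SVC only through CVP, the pooled value is a valid marginal quantity over a wider CVP range. It still depends on the share of clamped cases, and a larger anhepatic value would then reflect that wider range.

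Second, the per-time correlations are labelled informational and the interaction test is an additional analysis. That also stands. A reader might infer that the primary correlation is materially biased; step 3 does not support this at d = 1, and nothing in the documents indicates a larger shift.

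Third, the mix and the shifts are unknown. The mix is inferred from the wording of Aim 2, and Significance says the SVC response to clamping has not been studied. At d of 0.5 or less, or with nearly all or nearly no cases clamped, the effect is small.

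Fourth, a reader might infer that on-clamp readings undermine the use described as "Noninvasive measurement of PASP in mechanically ventilated patients with no central venous monitoring (not just in patients undergoing liver transplantation". That is a conditional remark under Significance. The hypothesis is limited to transplant recipients, no inference outside transplantation is planned, and the per-time reporting already gives four correlations without any anhepatic reading.

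**Conclusion.** The point holds in limited form. The plan cannot tell a change in correlation by phase from a mix of techniques within the anhepatic phase. This matters if both groups are sizeable and the clamp shifts are about 1 within-group SD or more: with half the cases clamped and d = 1 in the same direction, the anhepatic correlation rises by 0.10 to 0.20 for within-technique values of 0.5 to 0, and the interaction test rejects in 12% to 26% of runs against a nominal 2.5%. Below about 0.5 SD the effect is negligible. These sizes rest on the assumed p and d, and the rejection rates also on the assumed intraclass correlation and the stand-in test. The documents do not support calling the pooled correlation wrong or the primary result unsound. This is an inexpensive improvement to secondary and informational outputs.

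**What to change.** Record whether the IVC is clamped at the moment of the anhepatic reading; Aim 2 needs this field anyway. Keep the five-time repeated structure and all planned pooled analyses. Then add three items, labelled as sensitivity or descriptive:

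1. A version of the time-interaction test with a clamp-specific mean at the anhepatic time (a clamp-by-time fixed effect).
2. The anhepatic correlation by clamp status, beside the pooled one, with the number of patients in each group.
3. One estimate of the overall correlation without on-clamp readings.

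Do not split time into six repeated levels. No patient has both anhepatic states, so the unstructured covariance between them could not be estimated.

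The cost is precision in the clamp strata. At r = 0.5 the 99.5% interval is 0.26 to 0.68 with n = 100, 0.14 to 0.74 with n = 50, and 0.01 to 0.80 with n = 30. The stratum results should therefore be descriptive. Item 1 does not split the sample, so it remains usable if one group is small.
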